DOR will be described in tabular and graphical format using Kaplan-Meier methods by cohort. The Kaplan-Meier estimate of the distribution function will be constructed. Kaplan-Meier curves will be constructed. The number of patients at risk at certain time points will be shown on the plot. The estimated median (in months) along with 95% CIs, as well as 25th and 75th percentiles will be reported ([Brookmeyer and Crowley 1982](#)). In addition, Kaplan-Meier estimated probabilities with corresponding 95% CIs at several time points (including at least 3, 6, 9, 12 and 18 months) will be summarized by cohort. These analyses will be performed

separately based on BIRC assessment and based on investigator assessment. Refer to [Section 4.6.3](#) for further details regarding derivation of Kaplan-Meier estimates.

Disease control rate (DCR)

DCR is defined as the proportion of patients with best overall response of CR, PR, or SD per RECIST 1.1. DCR will be estimated and the binomial exact 95% CI will be provided by cohort. These analyses will be performed separately based on BIRC assessment and based on investigator assessment.

Time to response (TTR)

TTR is defined as the time from start of study drug to first documented response (CR or PR, which must be confirmed subsequently) for patients who achieved a confirmed PR or CR. All patients in the FAS will be included in time to response calculations. Patients who did not achieve a confirmed PR or CR, will be censored at:

- the maximum follow-up time (i.e. first patient first treatment to last patient last treatment by cohort used for the analysis) for patients who had a PFS event (i.e. either progressed or died due to any cause), or at the date of last adequate tumor assessment date otherwise.

TTR will be summarized in 6-weeks intervals using descriptive statistics. The distribution of time to response will be estimated using the Kaplan-Meier method and the median time to response will be presented along with 95% confidence interval only if a sufficient number of responses is observed. Failure curves (ascending Kaplan-Meier curves) will be constructed. These analyses will be performed separately based on BIRC assessment and based on investigator assessment.

Progression-free survival (PFS)

PFS is defined as the time from the start date of study drug to the date of the first radiologically documented PD or death due to any cause.

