2.8.2 Safety

All safety analyses will be performed based on the Safety Set by cohort and also for all patients. Safety will also be presented combining the MET mutant cohorts and amplified cohorts as defined in [Section 2.2](#).

Baseline

Baseline is the result of an investigation describing the “true” uninfluenced state of the patient. The last available assessment before or on the start date of study drug is defined as “baseline” value or “baseline” assessment. If an assessment is planned to be performed prior to the first dose of study drug in the protocol and the assessment is performed on the same day as the first administration of study drug, it will be assumed that it was performed prior to study drug administration, if assessment time point is not collected or is missing. If assessment time points are collected, the observed time point will be used to determine pre-dose on study day 1 for baseline calculation. Unscheduled assessments will be used in the determination of baseline. See [Section 4.7.2](#) for further details on derivation of baseline for laboratory data and ECGs.

Patients who start treatment and discontinue from the study on the same day may have 2 different sets of data collected on study day 1, one being reported to the cycle 1 day 1 visit, the other reported to the end of treatment (EOT) visit. Data reported at the EOT visit are not eligible for baseline selection.

Grouping for the analyses

The overall observation period will be divided into three mutually exclusive segments:

- Pre-treatment period: from day of patient’s informed consent to the day before first dose of study drug
- On-treatment period:
 - For discontinued patients, from day of first dose of study drug to 30 days after last dose of study drug
 - For ongoing patients, from day of first dose of study drug to the data cut-off date
- Post-treatment period: starting at day 31 after last dose of study drug

The safety summary tables will include only assessments collected no later than 30 days after study drug discontinuation and assessments prior to the data cut-off date for on-going patients, unless otherwise specified.

For select items, shift tables or change from baseline summaries generated for laboratory, ECG, vital signs and change score generation may use data from pre-treatment period for baseline calculations.

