- Central nervous system toxicity
- Pancreatitis
- Photosensitivity
- Teratogenicity
- Drug-drug interactions with strong CYP3A4 inducers
- QTc interval prolongation

This classification reflects the current version of the eCRS and might be updated based on review of accumulating data.

For each specified AESI, number and percentage of patients with at least one event of the AESI occurring during on treatment period will be summarized.

Summaries of these AESIs will be provided by cohort, (specifying grade, SAE, relationship, leading to permanent treatment discontinuation, leading to dose adjustment/interruption, death, etc.).

Analysis of time to first occurrence of any grade AESI will be applied as well as time to first occurrence of grade 3/4 AESI using the Kaplan-Meier method (see below the definitions). Duration of first occurrence of grade 3/4 AESI will also be summarized. These analyses will be performed for AESI regardless of study drug relationship and for AESI suspected to be study drug related.

For time to first occurrence, failure curves (ascending Kaplan-Meier curves) will be constructed in the combined MET mutant cohorts and all patients. Median together with 95% CI as well as 25th and 75th percentiles will be presented. In addition, the median time to occurrence for the subset of patients who experienced the event of interest will be calculated. Simple descriptive statistics (median, min and max, 25th and 75th percentiles) will be presented. The probabilities at selected time points and the associate 95% CI will also be summarized.

Duration of first occurrence of grade 3/4 AESI will be presented for the subset of patients who experienced the event. Failure curves (ascending Kaplan-Meier curves) will be constructed in the combined MET mutant cohorts and all patients. Median together with 95% CI as well as 25th and 75th percentiles will be presented.

Duration of first occurrence of an event will be presented for the subset of patients of the safety set who experienced the event. A patient will be censored for time to resolution, if there is no resolution during the on-treatment period. The same censoring rules as described below for time to first occurrence apply.

Time to first occurrence

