- Time to first occurrence of an event is defined as time from start of study treatment to the date of first occurrence of this event (or first event within an AE grouping), i.e. time in days is calculated as (start date of first occurrence of event) – (start of study treatment) +1.
- In the absence of an event during the on-treatment period, the censoring date applied will be the earliest of the following dates: death date, new anti-neoplastic antineoplastic therapy start date, end date of on-treatment, analysis cut-off date, and withdrawal of informed consent date. See [Section 2.7.1](#) for the definition of new anti-neoplastic antineoplastic therapy.

Duration of first occurrence (i.e. Time to resolution of an event)

- Duration of first occurrence of an event is defined as time from onset to the date of resolution of the first event: (date of resolution of first event) – (date of onset of event) + 1.
- Resolution of the event means that outcome of the Grade 3/4 event is “recovered/resolved”, “recovered/resolved with sequelae”, or “recovering/resolving” (returning to grade ≤ 2). The same preferred term as the 1st event identified is used to determine the resolution. The resolution occurring after end of treatment + 30 days will be considered.
- The date of resolution of first Grade 3/4 event is derived as follows:
 - = End date of the first Grade 3/4 event *if the first event is resolved* (i.e. duration of AE). If multiple Grade 3/4 events with the same start date are reported, the latest end date will be considered (i.e. the longest duration of AE).
 - = Start date of the 1st Grade ≤ 2 event *if the first event is improved*. If multiple Grade 3/4 events with the same start date are reported, the latest start date of the

1st Grade \leq 2 event will be considered (i.e. the longest duration of first occurrence).

- = Start date of the 1st Grade \leq 2 event *if the first event is worsened and then improved*, and no Grade 3/4 AE with an outcome “resolved/recovered” reported later on. If multiple Grade 3/4 events with the same start date are reported, the latest start date of the 1st Grade \leq 2 event will be considered (i.e. the longest duration of first occurrence).
- = End date of the Grade 3/4 event reported with outcome “recovered/resolved” *if the first event is worsened and then resolved* and Grade 3/4 AE with an outcome “resolved/recovered” reported.

With

- *Worsened: Event with a non-missing end date and outcome “not recovered/ not resolved”*

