- ALT or AST > 3×ULN & TBIL > 2×ULN & ALP < 2×ULN

Combined elevations values post-baseline (regardless of baseline levels)

- ALT or AST > 3×ULN & TBIL > 2×ULN
- ALT or AST > 3×ULN & TBIL > 2×ULN & ALP \geq 2×ULN
- ALT or AST > 3×ULN & TBIL > 2×ULN & ALP < 2×ULN

Combined elevations values post-baseline by baseline levels

AST/ALT \leq ULN at baseline

- ALT or AST > 3×ULN & TBIL > 2×ULN
- ALT or AST > 3×ULN & TBIL > 2×ULN & ALP \geq 2×ULN
- ALT or AST > 3×ULN & TBIL > 2×ULN & ALP < 2×ULN

AST/ALT > UNL at baseline

- Elevated ALT or AST & TBIL (>2×Baseline and 2×ULN)
- Elevated ALT or AST & TBIL (>2×Baseline and 2×ULN) & ALP \geq 2×ULN
- Elevated ALT or AST & TBIL (>2×Baseline and 2×ULN) & ALP < 2×ULN

with Elevated AST or ALT defined as: >3×ULN if \leq ULN at baseline, or (>3×Baseline or 8×ULN) if > ULN at baseline

In addition, a listing of all TBIL, ALT, AST and ALP values for patients with a post-baseline TBIL > 2×ULN, ALT > 3×ULN or AST > 3×ULN will be provided.

The relationship between post-baseline increases in ALT/AST and total bilirubin will be shown using eDISH plot: peak values of Total bilirubin vs peak values of ALT/AST at any time during the course of treatment (not necessarily concurrent).

Analysis of time to first occurrence of grade 3/4 AST/ALT (whichever occurs first) will be done. Time to first occurrence of grade 3/4 AST/ALT and duration of the first occurrence of grade 3/4 AST/ALT will be summarized using Kaplan-Meier method. Patients with grade 3/4 AST/ALT at baseline will be excluded from the analysis. Median together with 95% CI as well as 25th and 75th percentiles will be presented. In addition, the median time to occurrence for the subset of patients who experienced the event of interest will be calculated. Simple descriptive statistics

(median, min and max, 25th and 75th percentiles) will be presented. The probabilities at selected time points and the associate 95% CI will also be summarized.

Duration of first occurrence of grade 3/4 AST/ALT will be presented for the subset of patients who experienced the event. Median together with 95% CI as well as 25th and 75th percentiles will be presented.

ECGs

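### Time to first AESI is reported as 1 minus Kaplan-Meier with death, new therapy and end of treatment censored, so its time-point probabilities overstate on-treatment incidence

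*SAP*

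**What the plan says.** SAP 2.8.2 (Adverse events of special interest) analyses time to first AESI of any grade and "time to first occurrence of grade 3/4 AESI using the Kaplan-Meier method". On display it says: "For time to first occurrence, failure curves (ascending Kaplan-Meier curves) will be constructed in the combined MET mutant cohorts and all patients". Medians with 95% CI and quartiles are given. "The probabilities at selected time points and the associate 95% CI will also be summarized"; the time points are not named.

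Under Time to first occurrence, for a patient with no on-treatment event, "the censoring date applied will be the earliest of the following dates: death date, new anti-neoplastic antineoplastic therapy start date, end date of on-treatment". The list also includes the data cut-off and withdrawal of consent. The on-treatment period is defined earlier in 2.8.2: "For discontinued patients, from day of first dose of study drug to 30 days after last dose of study drug".

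The laboratory part of 2.8.2 has a parallel analysis. One sentence covers both time to first grade 3/4 AST/ALT and its duration: "duration of the first occurrence of grade 3/4 AST/ALT will be summarized using Kaplan-Meier method". It does not restate a censoring rule.

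Two other summaries bear on the same question. Section 2.8.2 also gives the number and percentage of patients with each AESI on treatment, and exposure-adjusted incidence rates for AEs. SAP 2.1 sets this analysis at Last Patient Last Visit. Neither document specifies a cumulative incidence function or any other competing-risks method.

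**The concern.** A patient who has died, or whose on-treatment period has ended, can no longer have an on-treatment AESI. Kaplan-Meier censoring treats that patient as still at risk, with the same future hazard as those who remain. The failure curve then estimates what would happen if nobody died or stopped drug, and only if those exits were unrelated to AESI risk. The SAP does not say that this is the quantity it wants.

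The time-point probabilities for hepatotoxicity, ILD/pneumonitis, pancreatitis and the rest would naturally be read as the share of treated patients affected by that time. The same report will carry the crude on-treatment percentage for each AESI, and the curve can rise above it with no explanation.

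**Working it through.** **No stated figure to reproduce.** The documents give no AESI probability, sample size or power for this analysis. The direction can be shown from the estimator. The size can only be illustrated.

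**Direction.** Take n patients, with every exit before an AESI being a competing event.
- The cumulative incidence (Aalen-Johansen) at time t is (number with an AESI by t)/n, so each event adds 1/n. It ends at the crude on-treatment percentage.
- Kaplan-Meier adds S(t−)/Y(t) at each event, where Y is the number still at risk. Each earlier exit passes its weight to those remaining, so the step is at least 1/n, and larger once any exit has come first.
- Hence 1 minus KM is never below the cumulative incidence. In simulation (four scenarios, n = 160 and n = 373 as in SAP 2.2, 1,000 trials each, 8,000 in all) there was no exception at 12 or 18 months.

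**Inputs for size.**
- AESI frequency p: 19.2% (creatinine increased, 58/302) and 4.0% (ALT increased grade 3/4, 12/302). The percentages are in Protocol 1.2.1.2.1 and the 302 in the Amendment 6 rationale. They are proxies for AESI rates.
- Median time to exit m: 3.55 and 7.39 months, the phase I median PFS values in Protocol 1.2.1.2.2, used as a stand-in for time on treatment. A 12-month median is a pure assumption.
- Exit is exponential. AESI onset has a constant hazard, or is early (Weibull shape 0.5, solved numerically). No administrative censoring.

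**Formulas, constant hazard.** d = ln 2/m; h = d·p/(1−p); 1−KM(t) = 1−exp(−ht); CIF(t) = p·[1−exp(−(h+d)t)].

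**Worked case, p = 19.2%, m = 7.39.** d = 0.6931/7.39 = 0.0938. h = 0.0938 × 0.192/0.808 = 0.0223.
- 12 months: 1−KM = 1−exp(−0.267) = 23.5%; CIF = 0.192 × [1−exp(−1.393)] = 14.4%.
- 18 months: 33.0% against 16.8%. With early onset, 27.5% against 18.2%. Both KM values exceed the 19.2% who ever have the event.
- The Kaplan-Meier first quartile falls at ln(4/3)/0.0223 = 12.9 months, although fewer than 25% of patients ever have the event.

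**Results at 12 months.**

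| Ever affected | Exit median (months) | Onset | 1−KM | CIF | Gap (points) |
|---|---|---|---|---|---|
| 19.2% | 3.55 | constant | 42.7% | 18.1% | 24.6 |
| 19.2% | 3.55 | early | 31.6% | 18.8% | 12.8 |
| 19.2% | 7.39 | constant | 23.5% | 14.4% | 9.1 |
| 19.2% | 7.39 | early | 23.1% | 17.1% | 6.0 |
| 19.2% | 12 | constant | 15.2% | 11.1% | 4.1 |
| 19.2% | 12 | early | 18.6% | 15.3% | 3.3 |
| 4.0% | 3.55 | constant | 9.3% | 3.7% | 5.6 |
| 4.0% | 7.39 | constant | 4.6% | 2.8% | 1.8 |
| 4.0% | 12 | early | 3.8% | 3.1% | 0.7 |

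The ratio runs from 18.6/15.3 = 1.2 to 9.3/3.7 = 2.5.

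**Adding the 30-day window.** Let every patient stay at risk for c = 30/30.4375 = 0.986 months after an exponential last-dose time. Then h solves 1 − exp(−hc)·d/(d+h) = p, and CIF(t) = 1−exp(−hc) + [h·exp(−hc)/(h+d)]·[1−exp(−(h+d)(t−c))]. For p = 19.2% and constant hazard at 12 months:
- m = 7.39: h = 0.0200, 21.4% against 14.3%.
- m = 3.55: h = 0.0376, 36.3% against 18.0%.

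The gap narrows but remains.

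**The case against.** **The overall question is already answered.** A reader might infer that the SAP overstates how many patients ever have each AESI. It does not: the crude on-treatment count and percentage is correct, and with no administrative censoring it equals the end value of the cumulative incidence. The exposure-adjusted rates are also sound. This stands. What remains wrong is the curve, the quartiles and the time-point values.

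**Kaplan-Meier may be a deliberate estimand.** Onset risk while exposed is a legitimate safety question, and cumulative incidence falls when patients leave treatment faster. This also stands in part. But that reading needs independent censoring and a label, and the SAP supplies neither.

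**Time to response.** SAP 2.8.1 assigns the maximum follow-up time to non-responders "for patients who had a PFS event (i.e. either progressed or died due to any cause". A reader might infer that the authors saw the problem and neglected it for safety. The documents do not show that. Protocol Appendix 1 (14.1.24) rests that rule on response no longer being possible, whereas stopping drug does not make liver injury or pneumonitis impossible. The parallel holds only because this endpoint is restricted to on-treatment events.

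**Size.** A reader might infer a known, several-fold overstatement at late times. The documents do not support one. Exposure is borrowed from phase I PFS, and treatment beyond progression is allowed. Far-out values also rest on few patients: with m = 3.55 and p = 19.2%, exp(−0.2416 × 18) = 1.3% remain at risk at 18 months. Medians will often not be reached for uncommon AESIs.

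**No decision depends on it.** The display is descriptive and single-arm. True, and this limits the weight of the point without removing it.

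**Conclusion.** The point holds as a limited one. For an on-treatment endpoint analysed at Last Patient Last Visit, the Kaplan-Meier failure curves and time-point probabilities are at or above the proportion of treated patients with an AESI by each time, and the quartiles come too early. The direction is a property of the estimator. The size is not derivable from the documents. Under the assumptions above, the 12-month ratio is about 1.2 to 2.5, and the absolute gap runs from under 1 point (rare AESI, early onset, long exposure) to about 25 points (common AESI, constant hazard, short exposure). No primary or key secondary efficacy result is touched.

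**What to change.** In SAP 2.8.2, make the Aalen-Johansen cumulative incidence the reported estimate for time to first AESI, any grade and grade 3/4.
- Competing events: death, start of new antineoplastic therapy, and permanent end of the on-treatment period.
- Censoring: analysis cut-off and consent withdrawal only. State that a patient whose in-study dosing ends only because the study closes (Protocol 4.3) counts as censored at cut-off.
- Apply the same method to time to first grade 3/4 AST/ALT, and write out its censoring rule.
- Name the time points.
- If Kaplan-Meier is kept, show it second, labelled as the hypothetical risk if all patients stayed alive and on treatment, assuming independent censoring.

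The cost is SAP wording and the EVENTCODE option in PROC LIFETEST, the procedure already named in SAP 4.6.3. Protocol 10.5.3.2 plans AE incidence tables and no Kaplan-Meier AESI analysis, so no protocol amendment is needed. The downside is that cumulative incidence depends on observed treatment duration, which is a reason to keep the labelled Kaplan-Meier display alongside.

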In addition, a summary of serious adverse events with number of occurrences will be produced (an occurrence is defined as >1 day between start and prior end date of record of same preferred term).

A listing will be provided to document any terms changed as a result of the re-mapping process to the latest MedDRA version available.

All AEs regardless of study drug relationship and all AEs suspected to be study drug related will be summarized by cohort and subgroup (as described in [Section 2.2](#)) using the safety set.

Exposure-adjusted overall incidence

The number and percentage of patients with any AEs along with the 95% confidence interval (95% CI) will be presented [[Clopper and Pearson 1934](#)]. In order to account for potential differences in exposure across groups, incidence rates of adverse events will be presented adjusted for Subject-Months exposure. [[Sahai and Khurshid, 1993](#); [Ulm 1990](#)].

The exposure-adjusted overall incidence rate is defined as the number of patients with an event divided by the corresponding sum of the exposure duration for all patients, where duration of exposure in Subject-Months is counted up to the first qualifying event (or end of time at risk for patients without event). AEs missing start date for exposure-adjusted overall incidence calculation is handled as follows: Start date of study drug will be considered as the AE start date for any AE with missing start date.

Adverse events of special interest

An adverse event of special interest is a grouping of adverse events that are of scientific and medical concern specific to compound INC280. These groupings are defined using MedDRA terms, SMQs (standardized MedDRA queries), HLGTs (high level group terms), HLT (high level terms) and PTs (preferred terms). Customized SMQs (Novartis MedDRA queries, NMQ) may also be used. A NMQ is a customized group of search terms which defines a medical concept for which there is no official SMQ available or the available SMQ does not completely fit the need. It may include a combination of single terms and/or an existing SMQ, narrow or broad.

All AESI definitions or AE grouping are specified in the electronic Case Retrieval Strategy (eCRS), in which they are identified by the flag “SP”. Additional AESI may be reported if there are any updates to the eCRS at the time of the analyses.

Adverse events of special interest (AESIs) INC280 are:

- Hepatotoxicity
- Renal dysfunction
- ILD/Pneumonitis

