4.7.4 Time to first occurrence of event and duration

This section provides additional details to those included in [Section 2.8.2](#). For each case, the start date and end date for the duration of the 1st occurrence are in bold.

Case 1a: First event resolved with a single event - Outcome = recovered/resolved

Patient ID	Preferred term	Start date	End date	Grade	Outcome
0001	INCREASED LIPASE	2016-05-31	2016-06-02	3	RECOVERED/RESOLVED

Case 1b: First event resolved with multiple events with the same start date - Outcome = recovered/ resolved

Patient ID	Preferred term	Start date	End date	Grade	Outcome
0002	INCREASED AMYLASE	2018-10-01	2018-10-29	3	RECOVERED/RESOLVED
	INCREASED LIPASE	2018-10-01	2018-11-20	3	RECOVERED/RESOLVED

Case 2a: The first event improved with a single event - Outcome = recovering/resolving

Patient ID	Preferred term	Start date	End date	Grade	Outcome
0003	ILD	2017-08-30	2017-09-20	3	RECOVERING/RESOLVING
	ILD	2017-09-21	2017-10-06	2	NOT RECOVERED/NOT RESOLVED
	ILD	2017-10-07		3	NOT RECOVERED/NOT RESOLVED

Case 2b: The first event improved with multiple events with the same start date - Outcome =recovering/resolving

Patient ID	Preferred term	Start date	End date	Grade	Outcome
0004	AST INCREASED	2017-11-30	2017-12-06	3	RECOVERING/RESOLVING
	HYPOALBUMINEMIA	2017-11-30	2017-12-06	2	RECOVERING/RESOLVING
	ALT INCREASED	2017-11-30	2017-12-13	3	RECOVERING/RESOLVING
	GGT INCREASED	2017-11-30	2018-01-12	2	RECOVERED/RESOLVED
	ALP INCREASED	2017-12-06	2017-12-13	1	RECOVERED/RESOLVED
	AST INCREASED	2017-12-06	2017-12-13	2	RECOVERING/RESOLVING
	ALT INCREASED	2017-12-13	2017-12-20	2	RECOVERING/RESOLVING
	AST INCREASED	2017-12-13	2017-12-20	1	RECOVERED/RESOLVED
	ALT INCREASED	2017-12-20	2018-01-12	1	NOT RECOVERED/NOT RESOLVED
	AST INCREASED	2018-01-12	2018-01-22	3	RECOVERING/RESOLVING
	ALT INCREASED	2018-01-12	2018-01-25	4	RECOVERING/RESOLVING

Case 2c: The first event improved (Gr 4, Gr 3 and Gr <3) - Outcome =recovering/resolving

Patient ID	Preferred term	Start date	End date	Grade	Outcome
0005	HEPATIC DYSFUNCTION	2017-01-06	2017-01-11	4	RECOVERING/RESOLVING
	HEPATIC DYSFUNCTION	2017-01-12	2017-01-18	3	RECOVERING/RESOLVING
	HEPATIC DYSFUNCTION	2017-01-19	2017-02-06	1	RECOVERED/RESOLVED

Case 3a: The first event worsened and then improved (Gr 3, Gr 4 and Gr <3) - Outcome =not recovered/not resolved and then recovering/resolving

Patient ID	Preferred term	Start date	End date	Grade	Outcome

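### The duration reported for a first grade 3/4 AESI can end while another grade 3/4 term of the same AESI is still active, because onset is set by the grouping and resolution by the first preferred term

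*SAP*

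**What the plan says.** All the rules are in SAP 2.8.2, with worked cases in SAP 4.7.4.

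- **Unit.** "An adverse event of special interest is a grouping of adverse events that are of scientific and medical concern specific to compound INC280". It is built from MedDRA queries, higher-level terms and preferred terms.
- **Output.** "Duration of first occurrence of grade 3/4 AESI will be presented for the subset of patients who experienced the event". It comes with Kaplan-Meier curves, the median and its 95% CI, and quartiles.
- **Onset.** Time to first occurrence runs to the "date of first occurrence of this event (or first event within an AE grouping"), so the clock starts at grouping level.
- **Duration.** "Duration of first occurrence of an event is defined as time from onset to the date of resolution of the first event", with one day added.
- **Resolution.** "The same preferred term as the 1st event identified is used to determine the resolution".
- **Ties.** "If multiple Grade 3/4 events with the same start date are reported, the latest end date will be considered". Where the event improves and does not fully resolve, the latest first record at grade 2 or below plays the same part. The SAP says that this choice gives the longest duration.

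The tie rule is shown on different preferred terms. "Case 1b: First event resolved with multiple events with the same start date" pairs amylase with lipase, and "Case 2b: The first event improved with multiple events with the same start date" pairs AST with ALT.

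**The concern.** Start and stop use different units. Any term in the grouping can start the clock, but only the term that started it can stop it, unless another grade 3/4 term began on the same date. The tie rule accepts that a grouped event is not over while another of its grade 3/4 terms persists. A second term that begins one day later loses that protection, although the clinical picture may be almost the same.

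The output is presented as the duration of a severe AESI. A reader of the study report would take it as the time a patient spends with that toxicity at grade 3/4. A patient whose first term settles enters the curve as resolved even if another grade 3/4 term of that AESI is ongoing or never resolves.

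**Working it through.** **Inputs (SAP 4.7.4, grade 3/4 records only)**

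| Case | Term | Grade 3/4 start | Resolution date under SAP 2.8.2 |
|---|---|---|---|
| 1b | Amylase | 2018-10-01 | 2018-10-29 (resolved) |
| 1b | Lipase | 2018-10-01 | 2018-11-20 (resolved) |
| 2b | AST | 2017-11-30 | 2017-12-06 (first grade ≤ 2) |
| 2b | ALT | 2017-11-30 | 2017-12-13 (first grade ≤ 2) |
| 3b | Amylase | 2017-09-12 | 2017-10-20 (first grade ≤ 2) |
| 3b | Lipase | 2017-10-26 | 2017-11-03 (resolved) |

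**Formulas**

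- Duration = resolution date − onset date + 1.
- SAP rule: onset is the earliest grade 3/4 start. Resolution is the latest resolution date among the terms that share that start date.
- Grouping-level rule: same onset. The end date is extended by each grade 3/4 term that starts on or before the current end. The episode stops when none remains active.

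**Step 1: the cases as written.** The SAP states no durations in the available text, so these are derived from its rules.

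- Case 1b: 2018-10-01 to 2018-11-20 = 51 days under both rules.
- Case 2b: 2017-11-30 to 2017-12-13 = 14 days under both rules.
- Case 3b: 2017-09-12 to 2017-10-20 = 39 days under both rules. Grade 3 lipase starts six days after amylase has fallen to grade 1, so nothing overlaps.

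**Step 2: move the start of the longer-lasting term and keep its end date.**

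| Case | Shift of longer term | SAP rule | Grouping-level rule |
|---|---|---|---|
| 1b | 1, 3 or 5 days | 29 days | 51 days |
| 2b | 1, 3 or 5 days | 7 days | 14 days |

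In Case 1b the difference is 51 − 29 = 22 days, or 22/51 = 43%, and grade 3 lipase is present throughout those 22 days. In Case 2b it is 14 − 7 = 7 days.

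**Step 3: move the shorter-lasting term by one day instead.** Both rules still give 51 and 14 days.

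**Step 4: direction.** Both rules share the same onset. The SAP end date is a maximum over the terms that start on that date. The grouping-level end date is a maximum over those terms plus any later overlapping ones. It can never be earlier, so the SAP rule equals or understates the grouping-level duration and cannot exceed it.

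**Step 5: coverage.** No rule in SAP 2.8.2 and no case in SAP 4.7.4 deals with a second grade 3/4 term that starts later, overlaps the first and outlasts it.

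**The case against.** The strongest reply is that the SAP does what it says. It defines the measure as resolution of the first event, so understatement exists only against a different measure. The same-preferred-term rule also has a proper job. Protocol 8.1.1 requires a new record when an event worsens and when a grade 3/4 event improves, so one toxicity is spread over several records that must be linked. On this view the same-date rule is only a tie-break for when the first event is not unique. Further, ALT, AST, amylase and lipase belong to one chemistry panel (Protocol Table 7-4), so abnormalities found on one draw would share an onset date and fall under the tie rule. Merging could also join separate events in a broad grouping. Finally, this is a descriptive summary with no decision attached, and listings and shift tables still show ongoing events.

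Much of this stands. The first-event definition is open, the linking role is real, and the 43% comes from a constructed shift. Two points remain. The output carries the AESI label, and the tie rule already looks across terms, so the plan is not consistently about one term. Staggered onset is also plausible: Protocol Table 6-4 asks for repeat liver tests, preferably within 48–72 hours, for many grade 3 and all grade 4 AST/ALT elevations, and for weekly amylase and lipase testing from grade 3. A second enzyme that reaches grade 3 at a repeat test would carry a later start date.

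A reader might infer that the reported medians are biased toward fast resolution, or that liver and pancreatic enzyme AESIs are the most affected. The documents do not support either. They give no count of staggered, overlapping terms, and nothing shows that these enzymes rise in sequence.

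**Conclusion.** The point holds as a gap in a descriptive safety summary. A grade 3/4 AESI can be counted as resolved while another grade 3/4 term of it is active. Relative to a grouping-level duration the error runs in one direction only. In the altered SAP examples it is 22 of 51 days and 7 of 14 days. In the examples as written it is zero.

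It needs all three conditions in the same patient: a second grade 3/4 term of the same AESI, a later start that overlaps the first, and a later end. How often this happens, and the effect on the median or quartiles, cannot be determined from the documents.

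The illustration assumes that amylase and lipase belong to one AESI, and likewise AST and ALT, as Cases 1b and 2b imply. The case retrieval strategy that holds the actual groupings is not available. SAP 4.7.4 marks the intended dates in bold, which the available text does not show, so the durations rest on the written rules. No efficacy conclusion is touched, and the priority is low.

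**What to change.** In SAP 2.8.2, keep the same-preferred-term rule for linking the records of one event. Then define the end of the first grade 3/4 AESI episode as the first date on which no grade 3/4 term of that AESI that began on or before the current end of the episode remains unresolved. Apply this whether or not start dates coincide, so that the tie rule becomes a special case. If an overlapping term does not resolve, the episode is unresolved and is censored under the existing rules.

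Add a worked case to SAP 4.7.4 with two overlapping terms and different start dates. Keep the first-preferred-term duration as a supplementary summary under that label.

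The cost is an interval merge on existing adverse event records. Cases 1b, 2b and 3b stay at 51, 14 and 39 days. The downsides are somewhat longer reported durations and the possible linking of separate terms in broad groupings. The supplementary summary lets a reader see how much the merge changes.
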